13.1.5 Presentation of Adverse Events

A listing of all adverse events starting at or after entering the Extension Period, including a flag for TEAEs will be included in the *addendum to CSR* based on the APTS_LT.

A similar listing of all adverse events occurring before entering the Extension Period will be produced for the *CSR* based on APRS.

For each period, an overview of the numbers and percentages of patients with TEAEs, serious adverse events (SAEs), TEAEs leading to infusion interruption, TEAEs leading to withdrawal, and of patients who died will be provided based on the APTS/APTS_LT. For TEAEs, SAEs, and TEAEs leading to withdrawal, the total number of events will be included.

13.1.6 Presentation of Treatment-emergent Adverse Events

The following summaries will be provided for the Placebo-controlled Period and for the Extension Period:

- TEAEs by SOC and preferred term
- TEAEs by preferred term
- TEAEs by sex and preferred term
- TEAEs with an incidence $\geq 2\%$ in any treatment group by preferred term
- causally related TEAEs by SOC and preferred term
- TEAEs by intensity (*mild/moderate/severe*), SOC, and preferred term

- causally related TEAEs by intensity, SOC, and preferred term
- TEAEs occurring on the day of dosing after infusion start by SOC and preferred term (this includes day of V2 and V5 infusion for the Placebo-controlled Period and day of V8, V11, V14, and V17 infusion for the Extension Period)

The summaries will be provided for the APTS for the Placebo-controlled Period and for APTS_LT for the Extension Period.

For the Extension Period, the two tables summarizing all TEAEs by SOC and preferred term and all TEAEs by preferred term will include two additional columns displaying the totals for eptinezumab 100 mg and eptinezumab 300 mg.

For TEAEs occurring on the day of dosing after infusion start, TEAEs with missing start times will also be included.

13.1.7 Presentation of Deaths

All the adverse events in patients who died before entering the Extension Period will be listed for the APRS for inclusion in the *CSR*.

All the adverse events in patients who died after entering the Extension Period will be listed for the APTS_LT for inclusion in the *addendum to CSR*.

13.1.8 Presentation of Serious Adverse Events

All SAEs occurring before entering the Extension Period will be listed for the APRS for inclusion in the *CSR*.

All SAEs occurring at or after entering the Extension Period will be listed for the APTS_LT for inclusion in the *addendum to CSR*.

Treatment-emergent SAEs will be summarized for the Placebo-controlled Period based on APTS and for the Extension Period based on APTS_LT by:

- SOC and preferred term
- preferred term

13.1.9 Presentation of Adverse Events Leading to Withdrawal

All AEs leading to withdrawal before entering the Extension Period will be listed for the APRS for inclusion in the *CSR*.

All AEs leading to withdrawal occurring at or after entering the Extension Period will be listed for the APTS_LT for inclusion in the *addendum to CSR*.
TEAEs leading to withdrawal will be summarized for the Placebo-controlled Period based on APTS and for the Extension Period based on APTS_LT by:

- SOC and preferred term
- preferred term

13.1.10 Presentation of Adverse Events Leading to Study Drug Infusion Interruption

All AEs leading to study drug infusion interruption before entering the Extension Period will be listed for the APRS for inclusion in the *CSR*.

All AEs leading to study drug infusion interruption occurring at or after entering the Extension Period will be listed for the APTS_LT for inclusion in the *addendum to CSR*.

TEAEs leading to study drug infusion interruption will be summarized for the Placebocontrolled Period based on APTS and for the Extension Period based on APTS_LT by:

- SOC and preferred term
- preferred term

13.1.11 Presentation of Adverse Events of Special Interest

Treatment-emergent adverse events of special interest (AESI) will consist of the preferred terms defined by the SMQs/HLTs/HLGTs listed in Table 6.

All AESIs occurring before entering the Extension Period will be listed for the APRS for inclusion in the *CSR*.

All AESIs occurring at or after entering the Extension Period will be listed for the APTS_LT for inclusion in the *addendum to CSR*.

The listings will be repeated for all AEs belonging to the Hypersensitivity and Anaphylactic Reactions event category only, see Table 6.

The following summaries of treatment-emergent AESIs will be provided for the Placebocontrolled Period and for the Extension Period:

- AESIs by SOC and preferred term
- AESIs by SOC and preferred term, separately for each individual event category

The summaries will be provided for the APTS for the Placebo-controlled Period and for APTS_LT for the Extension Period.

13.2 General Methodology for Other Safety Data

Unless otherwise specified, tables, graphs, and listings will be based on the APTS for the Placebo-controlled Period and APTS_LT for the Extension Period.

All tables and graphs will be presented by treatment group for the Placebo-controlled Period and by treatment sequence group for the Extension Period.

The denominators for the summaries of a given variable will be based on the number of patients with non-missing values at a given visit or during the assessment period.

Descriptive statistics for the safety variables, both absolute values and changes from baseline, will be presented by visit, separately for each period.

The number and percentage of patients with at least one PCS value at any post-baseline assessment time point will be summarized by variable, separately for each period. All available assessments in each period will be included in the evaluation of PCS values.

For patients with post-baseline PCS values in the Placebo-controlled Period, listings will be provided including all the values for those patients for the variable prior to entering the Extension Period, with flagging of PCS values and out-of-reference-range values for inclusion in the *CSR*.

For patients with PCS values occurring after start of V8 IMP infusion, similar listings will be provided including all the values for those patients for the variable for inclusion in the *addendum to CSR*.

For inclusion in the *CSR*, all the adverse events occurring before entering the Extension Period in patients with post-baseline PCS values in the Placebo-controlled Period will be listed by treatment group and patient screening number; the listing will include the PCS value, the assessment date, the change from baseline in PCS value, the preferred term for the adverse event, and start date and stop date of the adverse event. The PCS values and adverse events will be listed in chronological order according to assessment date and the start date of the adverse event.

Similar listings will be provided for patients with PCS values occurring after start of V8 IMP infusion, including all the adverse events for the patients, for inclusion in the *addendum to CSR*.

For urine dipsticks, for which the results are categorical values (for example, negative, trace, 1+, 2+), the number and percentage of patients will be summarized by visit for each test, separately for each period. The microscopy results will be listed by assessment time point for patients with findings.

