4.2 Definition of Baseline

For migraine and headache endpoints, the baseline value will be based upon the data recorded in the headache eDiary during the first 28 days following screening.

For other endpoints, the baseline assessment will be the latest available valid measurement taken prior to the administration of IMP.

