13.3 Clinical Safety Laboratory Test Data

13.3.1 Data Presentation

The PCS criteria used for the clinical safety laboratory tests can be found in Table 3.

The clinical safety laboratory test values will be presented both in conventional and Système International (SI) units.

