Appendix V PCS Criteria

PCS Criteria

Laboratory Test	CDISC Term	Unit	PCS Low	PCS High
Haematology / Coagulation				
B-haemoglobin	HGB	g/L	\leq 95 (women)	\geq 165 (women)
			\leq 115 (men)	\geq 185 (men)
B-erythrocytes (red cell count)	RBC	x 10E12/L	\leq 3.5 (women)	\geq 6.0 (women)
			\leq 3.8 (men)	\geq 7.0 (men)
B-haematocrit (packed cell volume)	НСТ	V/V	\leq 0.32 (women)	\geq 0.50 (women)
			\leq 0.37 (men)	\geq 0.55 (men)
B-MCV (mean cell volume)	MCV	fL	\leq 0.8 x LLN	\geq 1.2 x ULN
B-total leucocyte (white cell count)	WBC	x 10E9/L	≤2.8	≥16
B-neutrophils/leucocytes	NEUTLE	%	≤ 20	≥ 85
B-eosinophils/leucocytes	EOSLE	%		≥ 10
B-basophils/leucocytes	BASOLE	%		≥ 10
B-lymphocytes/leucocytes	LYMLE	%	≤ 10	\geq 75
B-monocytes/leucocytes	MONOLE	%		≥15
B-thrombocytes (platelet count)	PLAT	x 10E9/L	≤ 75	≥ 600
P-INR (prothrombin ratio)	INR	Ratio		≥ 2.0
B-prothrombin time	PT	Sec		≥ 18
Liver				
S-aspartate aminotransferase	AST	U/L		\geq 3 × ULN
S-alanine aminotransferase	ALT	U/L		\geq 3 × ULN
S-bilirubin	BILI	µmol/L		\geq 34
S-bilirubin, direct	BILDIR	µmol/L		≥12
S-bilirubin, indirect	BILIND	µmol/L		\geq 22
S-alkaline phosphatase	ALP	U/L		\geq 3 × ULN
S-gamma glutamyl transferase	GGT	U/L		\geq 200
S-alpha-glutathione S-transferase (alpha-GST)	GSTAL	µg/L		≥20
Kidney				
S-creatinine	CREAT	µmol/L		$\geq 1.5 \text{ x ULN}$
B-urea nitrogen (BUN)	BUN	mmol/L		≥ 11
S-uric acid (urate)	URATE	µmol/L		\geq 510 (women)
				\geq 630 (men)
Electrolytes				
S-sodium (natrium)	SODIUM	mmol/L	≤ 125	≥155
S-potassium (kalium)	Κ	mmol/L	≤ 3.0	≥ 6.0

Table 3 PCS Criteria for Clinical Safety Laboratory Tests

Laboratory Test	CDISC Term	Unit	PCS Low	PCS High
S-calcium	CA	mmol/L	≤ 1.8	≥ 3.0
S-chloride	CL	mmol/L	≤ 1.8 ≤ 90	≥ 3.0 ≥ 117
S-magnesium	MG	mmol/L	≤ 90 ≤ 0.6	≥ 1.7 ≥ 1.3
S-phosphate (phosphorus,	PHOS	mmol/L	≤ 0.65	≥ 1.3 ≥ 1.95
(inorganic)	rnos	IIIII01/L	≤ 0.05	≥ 1.95
S-bicarbonate	BICARB	mmol/L	≤ 12	≥ 38
Endocrine / Metabolic				
B-glucose, non-fasting/unknown	GLUC	mmol/L	≤ 3.4	≥9.4
B-glucose, fasting	GLUC	mmol/L	≤ 3.0	≥ 6.0
S-glucose, non-fasting/unknown	GLUC	mmol/L	\leq 3.9	≥ 11.1
S-glucose, fasting	GLUC	mmol/L	≤ 3.5	≥ 7.0
B-glycosylated haemoglobin, fasting	HBA1C	Hb fract.		≥ 0.065
S-prolactin	PROLCTN	mIU/L		≥ 1350
S-thyrotropin/TSH	TSH	mIU/L	≤ 0.3	≥ 5.5
S-protein (total)	PROT	g/L	\leq 45	≥95
S-albumin	ALB	g/L	≤ 27	
Lipids				
S-cholesterol total, non- fasting/unknown	CHOL	mmol/L		≥ 7.8
S-cholesterol total, fasting	CHOL	mmol/L		≥ 6.2

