S-triglycerides, non- fasting/unknown	TRIG	mmol/L		≥ 5.65
S-triglycerides, fasting	TRIG	mmol/L		\geq 4.2
S-LDL cholesterol, non- fasting/unknown	LDL	mmol/L		≥ 5.3
S-LDL cholesterol, fasting	LDL	mmol/L		\geq 4.9
S-HDL cholesterol, non- fasting/unknown	HDL	mmol/L	≤ 0.8	
S-HDL cholesterol, fasting	HDL	mmol/L	≤ 0.9	
Cardiac/Skeletal/Muscle				
S-creatine kinase (total)	CK	U/L		\geq 400 (women) \geq 750 (men)
S-creatine kinase MB isoenzyme	CKMB	μg/L		$\geq 8.5 \text{ or}$
5	CKMBCK	%		\geq 3.5% of total CK
S-lactate dehydrogenase (total)	LDH	IU/L		≥ 750
S-troponin I	TROPONI	µg/L		≥ 1.5
S-troponin T	TROPONT	μg/L		≥ 0.4
Infection		-		
S-C-reactive protein	CRP	mg/L		≥25
S-globulin (total)	GLOBUL	g/L	≤15	≥ 55

Laboratory Test	CDISC Term	Unit	PCS Low	PCS High
Urine				
Urinary pH	PH		\leq 4	≥ 9

Table 4 PCS Criteria for Vital Signs, Weight/BMI, and Waist Circumference

Variable	CDISC Term	Unit	PCS Low	PCS High
Waist circumference	WSTCIR	Cm	decrease $\geq 7\%$	increase $\geq 7\%$
Weight	WEIGHT	Kg	decrease $\geq 7\%$	increase $\geq 7\%$
Body Mass Index	BMI	kg/m2	decrease $\geq 7\%$	increase $\geq 7\%$
Pulse rate, supine/sitting/unknown	PULSE	beats/min	< 50 and decrease ≥ 15	\geq 120 and increase \geq 15
Diastolic blood pressure, supine/sitting/unknown	DIABP	mmHg	≤ 50 and decrease ≥ 15	\geq 105 and increase \geq 15
Systolic blood pressure, supine/sitting/unknown	SYSBP	mmHg	\leq 90 and decrease \geq 20	\geq 180 and increase \geq 20
Orthostatic systolic blood pressure	OBP	mmHg	≤ -30	
Orthostatic pulse rate	OPR	beats/min		≥ 20
Temperature	TEMP	°C	decrease ≥ 2	\geq 38.3 and increase \geq 2

Increase/decrease is relative to the baseline value.

Table 5PCS Criteria for ECG Parameters

ECG Parameter	CDISC Term	Unit	PCS Low	PCS High
Absolute Time Interval				
PR interval	PRAG	Msec		≥ 260
QRS interval	QRSAG	Msec		≥ 150
QT interval	QTAG	Msec		\geq 500
Derived Time Interval				
Heart rate	EGHRMN	beats/min	< 50 and decrease ≥ 15	\geq 120 and increase \geq 15
QTcB interval	QTCBAG	Msec	< 300	> 500 or increase > 60
QTcF interval	QTCFAG	Msec	< 300	> 500 or increase > 60

Increase/decrease is relative to the baseline value.

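### The laboratory PCS summary in SAP 13.2 does not separate new from pre-existing abnormalities, which dilutes the relative difference between arms

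*SAP*

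**What the plan says.** SAP 13.2 defines the PCS summary as follows: "The number and percentage of patients with at least one PCS value at any post-baseline assessment time point will be summarized by variable". The Placebo-controlled and Extension Periods each get their own table. On which values enter, it says: "All available assessments in each period will be included in the evaluation of PCS values". On the percentage base it says: "The denominators for the summaries of a given variable will be based on the number of patients with non-missing values at a given visit"; the same sentence extends this to the assessment period. Neither numerator nor denominator depends on whether the patient was PCS at baseline.

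For laboratory data, SAP 13.3.1 says: "The PCS criteria used for the clinical safety laboratory tests can be found in Table 3". Every entry there is a fixed limit or a multiple of LLN or ULN. The row "S-cholesterol total, fasting", for example, is PCS at 6.2 mmol/L or more, whatever the patient's starting value. Tables 4 and 5 differ: weight, pulse, blood pressure, temperature, heart rate and QTc carry change conditions, with the footnote "Increase/decrease is relative to the baseline value". Table 3 has no such condition.

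A baseline value is available for safety variables. SAP 4.2 says: "the baseline assessment will be the latest available valid measurement taken prior to the administration of IMP". Laboratory samples are scheduled at screening and before the Baseline Visit infusion.

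For patients with a post-baseline PCS value in the Placebo-controlled Period, SAP 13.2 also plans patient-level output: "listings will be provided including all the values for those patients for the variable prior to entering the Extension Period". PCS and out-of-range values are flagged there. A further listing sets PCS values and their change from baseline beside the patient's adverse events. The only shift tables in the SAP are for EQ-5D-5L items (12.5).

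**The concern.** PCS values are a named safety endpoint in the protocol and the SAP. A reader of the PCS table wants to know how many patients became abnormal on each treatment. The table instead adds those patients to the ones who arrived abnormal and stayed so. Randomization makes the second group about equal across arms, so it adds a similar constant to each percentage and pulls the ratio towards 1.

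The SAP handles this elsewhere: adverse events are split into pre-treatment and treatment-emergent (13.1.3), and most vital-sign criteria require a change. Laboratory PCS values have no equivalent rule.

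The Extension Period adds a second difficulty. It has no placebo arm to balance pre-existing cases. The SAP also does not say whether the reference there is the value before the first infusion or before the Visit 8 infusion. A placebo patient who became PCS before Visit 8 and remains so would count as a PCS case in the period on eptinezumab.

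**Working it through.** The documents state no PCS rate, so there is no figure of the plan's own to reproduce. The size can only be illustrated.

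**Inputs**
- n = 280 planned per arm (protocol 3.1).
- b = share PCS at baseline: assumed 2% to 20%, equal across arms.
- s = share of those with a PCS value again after baseline: assumed 1.0 or 0.7, equal across arms.
- p = share newly PCS among patients not PCS at baseline: assumed 3% on placebo and 6% on active, with 1% and 4% as a second case.

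**Formulas**
- SAP 13.2 count: b·s + (1 − b)·p.
- Treatment-emergent count: p, over the n(1 − b) patients at risk.
- Absolute difference as the SAP counts: (1 − b)·(p_active − p_placebo), because b·s cancels.

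**3% versus 6%, s = 1** (treatment-emergent ratio 2.0, difference 3.0 points)

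| b | Placebo | Active | Ratio | Difference (points) |
|---|---|---|---|---|
| 2% | 4.94% | 7.88% | 1.60 | 2.94 |
| 5% | 7.85% | 10.70% | 1.36 | 2.85 |
| 10% | 12.70% | 15.40% | 1.21 | 2.70 |
| 15% | 17.55% | 20.10% | 1.15 | 2.55 |
| 20% | 22.40% | 24.80% | 1.11 | 2.40 |

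The 15% row in full: 0.15 + 0.85 × 0.03 = 0.1755 and 0.15 + 0.85 × 0.06 = 0.2010. In patients, 0.15 × 280 = 42 per arm are already PCS and 238 are at risk, giving 42 + 7.1 = 49.1 versus 42 + 14.3 = 56.3. The excess of 7.1 patients is the same under either count; only the background changes.

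As a gauge of noise, z for the SAP count is 0.0255 / √[(0.1755 × 0.8245 + 0.2010 × 0.7990)/280] = 0.77. For the treatment-emergent count it is 0.03 / √[(0.03 × 0.97 + 0.06 × 0.94)/238] = 1.58. Neither reaches 1.96.

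**1% versus 4%** (treatment-emergent ratio 4.0)

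| b | Ratio, s = 1 | Ratio, s = 0.7 |
|---|---|---|
| 2% | 1.99 | 2.24 |
| 5% | 1.48 | 1.64 |
| 10% | 1.25 | 1.34 |
| 20% | 1.12 | 1.16 |

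At b = 0 the two counts agree.

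**Which tests are exposed.** Exclusion criterion 22 bars screening ALT or AST above 2×ULN and creatinine above 1.5×ULN. The PCS limits are 3×ULN and 1.5×ULN or more, so b should be near zero for these. Lipids, glucose, HbA1c, CK, GGT and eosinophils have no numeric eligibility limit.

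**The case against.** The strongest reply is that other planned outputs show new cases.
- The flagged listings include each such patient's baseline value.
- The second listing gives the change from baseline.
- Change-from-baseline statistics are tabulated by visit.
- Protocol 9.4.2 requires any out-of-range value judged clinically significant to be recorded as an adverse event. If it starts or worsens after the first dose, it enters the TEAE tables by arm.

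The plan also delivers what the protocol asks, which is that PCS values be flagged and summarized, and counting any post-baseline PCS value omits nobody. A table limited to patients at risk would drop those already PCS who worsen further. No test of PCS rates is planned, so a smaller z changes no decision.

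All of this stands, and it rules out a stronger reading. A reader might infer that new abnormalities are hidden, or that the table mostly describes who was enrolled. The documents do not support either: the listings and TEAE route expose new cases, and the absolute difference is largely preserved.

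Nor do they show that baseline PCS values are common. Criterion 22 also excludes any out-of-range value that is a potential safety risk, and criterion 17 covers clinically relevant hepatic, endocrinological and haematological disorders. Sampling is fasting only when possible, and the non-fasting limits are higher (cholesterol 7.8 against 6.2, blood glucose 9.4 against 6.0 mmol/L).

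What remains is a gap at summary level. The listings cover only patients with a post-baseline PCS value, so they do not supply the at-risk denominator. Mean changes do not show who crossed a limit. The TEAE route depends on investigator judgement.

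**Conclusion.** The point holds for the laboratory PCS summary, as dilution of the relative difference between arms. The reading of the text is certain: no baseline condition in the numerator, the denominator or Table 3, and no laboratory shift table. The size is not known, because the documents give no baseline prevalence, persistence or emergent rate. Under 3% versus 6% with full persistence, a ratio of 2.0 appears as 1.60 at 2% prevalence and 1.11 at 20%, while the absolute difference falls only from 3.0 to between 2.94 and 2.40 points. Lower persistence weakens the effect. It is small for ALT, AST and creatinine, and potentially larger for tests without a numeric eligibility limit. Efficacy conclusions and formal tests are not touched. The change is still worth making, because the table reports a named safety endpoint and the remedy uses data already collected.

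**What to change.** In SAP 13.2, for laboratory variables, add a treatment-emergent PCS summary by variable and period:
- **Numerator:** patients with a first PCS value, in the given direction, after baseline.
- **Denominator:** patients not PCS in that direction at baseline and with at least one post-baseline value.

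A shift table of baseline against worst post-baseline PCS status would serve equally well.

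Keep the present all-patient count beside it, so that patients already PCS who worsen are not lost. State which value is the reference for the Extension Period, in particular for patients switching from placebo.

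The cost is SAP wording, one flag in the safety datasets, extra table columns and slightly smaller denominators in the added summary. No new data are needed.

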	 Response: patients with 100% reduction from baseline in monthly migraine days
	 Response: patients with 50% reduction from baseline in monthly headache days
	 Response: patients with 75% reduction from baseline in monthly headache days
	 Response: patients with 100% reduction from baseline in monthly headache days
	- Migraine/headaches with severe pain intensity
	 Change from baseline in the number of monthly migraine days with use of acute medication
	– PGIC score
	 Change from baseline in the number of monthly migraine days in patients with MOH
	- Patients with a migraine on the day after first dosing
	 Change from baseline in MBS score
	 Change from baseline in monthly number of Migraine attacks for each 12-week period
	 Change from baseline in monthly number of Headache episodes for each 12-week period
	- Change from baseline in the MSQ v2.1 sub-scores
	- Change from baseline in the EQ-5D-5L VAS score
	- Change from baseline in HCRU
	 Change from baseline in WPAI sub-scores
Safety Objective	Safety Endpoints
• To evaluate the safety and tolerability of	– Adverse events
eptinezumabTo evaluate the long-term safety and tolerability of eptinezumab	 Absolute values and changes from baseline in clinical safety laboratory test values, vital signs, weight, and ECG parameter values
	 Potentially clinically significant clinical safety laboratory test values, vital signs, weight changes, and ECG parameter values
	 Development of specific anti-eptinezumab antibodies (ADA) including neutralizing antibodies (NAbs)
	- Columbia-Suicide Severity Rating Scale (C-SSRS) score

Study Methodology

- This is an interventional, multi-national, multi-site, randomized, double-blind, placebo-controlled Phase IIIb study designed to demonstrate efficacy and safety of eptinezumab for migraine prevention in patients with unsuccessful prior preventive treatments. The placebo-controlled period will be followed by an extension period where all patients will receive active treatment to assess the long-term safety, tolerability and effect of eptinezumab.
- The total study duration from the Screening Visit to the Completion Visit is approximately 76 weeks and includes a Screening Period (28-30 days), Placebo-controlled Period (24 weeks) and Extension Period (48 weeks).

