16.7 Exposure

Number of infusions in the Placebo-controlled Period (infusions at Visit 2 and visit 5), and number of infusions in the Extension Period (infusions at Visit 8, Visit 11, Visit 14, and Visit 17) will be summarized.

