4.1 Definition of Periods

The study consists of the following periods:

- *Screening Period* (28-30 days): Starts at the Screening Visit and continues up to start of Visit 2 IMP infusion
- *Placebo-Controlled Period*: Starts at start of Visit 2 IMP infusion and continues up to start of Visit 8 IMP infusion
- *Extension Period*: Starts at start of Visit 8 IMP infusion and continues up to and including Visit 20

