13.1 Adverse Events

13.1.1 General Methodology for Adverse Events

Unless otherwise specified, tables, graphs, and listings will be based on the APTS for the Placebo-controlled Period and the APTS_LT for the Extension Period.

All the tables and graphs will be presented by treatment group for the Placebo-controlled Period and by treatment sequence group for the Extension Period, unless otherwise specified.

Tables by preferred term and tables by system organ class (SOC) and preferred term will be sorted in descending order based on the percentages of patients with these adverse events in the eptinezumab 300 mg dose group.

Unless otherwise specified, the summaries of adverse events will include the number and percentage of patients with an adverse event. In tables displaying SOC or preferred terms, patients are counted only once within each SOC or preferred term.

Listings of adverse events will be sorted by site, treatment group, patient screening number, and adverse event start date, and include preferred term, investigator term, adverse event start date, the date of first IMP infusion, the date and time of the latest IMP infusion prior to the adverse event, the time since latest IMP infusion, duration of the adverse event, date of death, action taken, causality, intensity, seriousness, and outcome. For adverse events that change in intensity, each intensity will be included. In listings of adverse events, start or stop dates will be displayed as collected also in case of partially or completely missing dates.

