13.6 Other Safety Endpoints

13.6.1 Columbia-Suicide Severity Rating Scale (C-SSRS) Scores

The C-SSRS was administered:

- for lifetime (using the *Baseline/Screening Version*) the C-SSRS assessment at screening that collects a lifetime recall
- for the past 12 months at screening (using the *Baseline/Screening Version*) the C-SSRS assessment at screening that focuses on the last 12 months
- at baseline (using the *Since Last Visit Version*) the C-SSRS assessment at baseline that collects information since the previous visit
- post-baseline (using the Since Last Visit Version) the C-SSRS assessments after baseline

The numbers and percentages of patients with lifetime, past 12 months, baseline, or postbaseline suicide-related events based on the C-SSRS will be summarized by treatment group. For each summary, the most severe item with an answer "Yes" for each patient according to the ordering given in Panel 4 is displayed. For the post-baseline assessments, the summaries will be by treatment group and period and the most severe item with an answer "Yes" for the whole period for each patient related to suicidal ideation and/or behaviour will be summarized.

The number and percentage of patients with *no suicidal ideation or behaviour* will be included in the summaries.

C-SSRS Score		Related to:	
1	Wish to be dead	Suicidal ideation	
2	Non-specific active suicidal thoughts		
3	Active suicidal ideation with any methods (not plan) without intent to act		
4	Active suicidal ideation with some intent to act, without specific plan		
5	Active suicidal ideation with specific plan and intent		
6	Preparatory acts or behaviour	Suicidal behaviour	
7	Aborted attempt		
8	Interrupted attempt		
9	Non-fatal suicide attempt		
10	Completed suicide (only applicable for the post-baseline assessments)		

Panel 4	C-SSRS Scores
	C-BBIG BUILS

The C-SSRS scores will be summarized based on the APTS for the lifetime, past 12 months, baseline and Placebo-controlled Period summaries and based on the APTS_LT for the

Extension Period summary. Patients with at least one C-SSRS assessment in the period will be included, regardless of whether they had a baseline C-SSRS assessment.

Missing C-SSRS scores will not be imputed.

Positive responses to non-suicidal self-injurious behaviour will be summarized separately.

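### Cumulative safety percentages cover 24 weeks and 2 infusions in the Placebo-controlled Period but 48 weeks and 4 infusions in the Extension, with no exposure adjustment, so they are not comparable between periods

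*SAP*

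**What the plan says.** Protocol section 3.1 gives the lengths: "Screening Period (28-30 days), Placebo-controlled Period (24 weeks) and Extension Period (48 weeks"). Protocol 16.7 counts the infusions. For the first period it names two: "Number of infusions in the Placebo-controlled Period (infusions at Visit 2 and visit 5"). For the second it lists four, at Visits 8, 11, 14 and 17. SAP 4.1 defines the Extension as the interval that "Starts at start of Visit 8 IMP infusion and continues up to and including Visit 20", that is, Week 24 to Week 72.

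The safety summaries are made separately for each period, and most of the incidence tables count a patient once:

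- **Adverse events (SAP 13.1.1):** "the summaries of adverse events will include the number and percentage of patients with an adverse event". This governs the TEAE, SAE and AESI tables in 13.1.5 to 13.1.11.
- **Dosing-day TEAEs (SAP 13.1.6):** "this includes day of V2 and V5 infusion for the Placebo-controlled Period and day of V8, V11, V14, and V17 infusion", where the last four days belong to the Extension.
- **Potentially clinically significant (PCS) values (SAP 13.2):** "number and percentage of patients with at least one PCS value at any post-baseline assessment time point". Every assessment in the period counts, and the denominator is patients.
- **Liver-injury (DILI) criteria (SAP 13.3.3):** met at any post-baseline visit, by period.
- **C-SSRS (SAP 13.6.1):** the most severe positive item "for the whole period for each patient related to suicidal ideation and/or behaviour will be summarized".

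Exposure (SAP 10) is reported as infusion counts and durations. Kaplan-Meier curves are planned only for time to withdrawal (SAP 7.2). Neither document plans an event rate per unit of patient-time or per infusion.

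**The concern.** Both documents list long-term safety and tolerability as a safety objective. All Extension patients receive eptinezumab, so there is no concurrent placebo group. A reader of the addendum will naturally set an Extension percentage beside the corresponding Placebo-controlled one to see whether risk changes with longer treatment.

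For a cumulative percentage, that comparison mixes the event rate with the length of the window. An unchanged rate, or one that has fallen moderately, can show as a higher percentage. Patients switching from placebo are affected too: their first percentage on active drug covers 48 weeks, while that of patients randomized to eptinezumab covers 24.

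**Working it through.** **Opportunity in each period**

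| | Placebo-controlled | Extension | Ratio |
|---|---|---|---|
| Weeks | 24 - 0 = 24 | 72 - 24 = 48 | 2 |
| Infusions | 2 (V2, V5) | 4 (V8, V11, V14, V17) | 2 |
| Scheduled post-baseline laboratory, ECG and C-SSRS visits | 2 (V5, V8) | 4 (V11, V14, V17, V20) | 2 |
| Post-baseline vital-sign slots (SAP Panels 12 and 13) | 4 | 8 | 2 |

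The plan's own total is reproduced: 4 + 24 + 48 = 76 weeks, as the protocol states.

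**Constant hazard, full follow-up.** If a proportion p has the event in 24 weeks, the proportion over 48 weeks is 1 - (1 - p)². Divided by p, this gives a ratio of 2 - p.

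| p in 24 weeks (assumed) | 48 weeks | Ratio |
|---|---|---|
| 1% | 1.99% | 1.99 |
| 5% | 9.75% | 1.95 |
| 10% | 19% | 1.90 |
| 20% | 36% | 1.80 |
| 40% | 64% | 1.60 |
| 60% | 84% | 1.40 |

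Per unit of time nothing has changed. For p = 5%, the rate is -ln(0.95)/(24/52.18) = 0.1115 per patient-year, or 11.2 per 100 patient-years, in both periods.

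**Falling hazard.** With the hazard reduced by a fraction r, the Extension percentage is 1 - exp(-2(1 - r)h), where h = -ln(1 - p). At r = 40%, 5% still becomes 6.0% and 40% becomes 45.8%. At r = 50% the two percentages are equal; beyond that the Extension figure is lower.

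**Departures from the simple case.** The documents give none of these inputs, so all are assumptions.

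- *Dropout.* With 5% to 20% leaving uniformly over the Extension, the ratio is 1.90 to 1.76 at p = 5% and 1.57 to 1.47 at p = 40%.
- *Correlated repeat assessments.* With 2 versus 4 looks, a 5% chance per look and a beta-binomial model, within-patient correlations of 0.1, 0.3, 0.5 and 0.8 give ratios of 1.75, 1.53, 1.36 and 1.15.
- *Risk concentrated at the first infusion.* Take a 2% risk at the first infusion and a fraction f of that at each later one. For patients continuing on eptinezumab, the Placebo-controlled percentage is 1 - 0.98(1 - 0.02f) and the Extension percentage is 1 - (1 - 0.02f)⁴. The ratios are 1.32 at f = 50%, 0.80 at 25% and 0.36 at 10%. For switchers, whose first active infusion falls in the Extension, the ratios to the eptinezumab groups' Placebo-controlled percentage are 1.65, 1.39 and 1.18.

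**The 2% table.** SAP 13.1.6 uses the same 2% cut-off in both periods. At constant hazard, an event at 1 - √0.98 = 1.005% per 24 weeks reaches 2% in 48 weeks.

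**The case against.** A reader might infer that Extension rates roughly double by construction. The documents do not support that. Only observation time, infusions and scheduled assessments double. The percentage comes close to doubling only for uncommon events with constant hazard, little dropout and little correlation between assessments. Vital-sign slots include pre- and post-dose readings from the same visit, so correlation there is likely.

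A reader might also infer that Extension percentages can be interpreted only against the earlier period. That too goes further than the SAP. It plans no formal between-period comparison and reports the Extension in a separate addendum. Its Extension safety tables are by treatment sequence, giving four groups with the same planned 48 weeks, so dose and prior-exposure contrasts are available at equal planned length.

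Part of the needed material is already planned. SAP 13.1.5 gives total event counts for TEAEs, SAEs and TEAEs leading to withdrawal. SAP 10 gives infusions received. Laboratory, vital-sign and ECG descriptives, QTcF categories and ADA results are by visit and do not accumulate. Complete TEAE tables stand beside the 2% extract, so crossing that cut-off neither hides nor creates a signal.

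Finally, exposure adjustment does not make the two populations alike. The long-term treated set requires a visit in the Extension, and Protocol 5.4 withdraws patients for several safety reasons.

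All of this stands and limits the point. It does not supply a measure that can be read across periods, and the sequence groups cannot show whether risk under eptinezumab differs between the first 24 weeks and later.

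**Conclusion.** The point holds as one of comparability. The cumulative safety percentages rest on twice the time and twice the infusions in the Extension, no adjustment is planned, and they should not be compared between periods as they stand. Under constant hazard and full follow-up the distortion is a factor of 2 - p: about 1.8 to 2.0 for events at or below 20% per 24 weeks, and about 1.4 to 1.6 at 40% to 60%. Those event rates are illustrative. Under the other assumed scenarios the factor is smaller and can be below 1. Because it differs by event type, no single mental correction works.

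Comparisons between groups within a period are not affected by the difference in planned length, and no efficacy result or significance test is involved. This is a low-cost improvement to what the addendum can say about long-term safety.

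**What to change.** In SAP 13.1.5 to 13.1.11, 13.2, 13.3.3 and 13.6.1, keep the planned percentages and add:

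1. For the main AE, SAE and AESI tables, patients with events per 100 patient-years, by period.
2. For dosing-day TEAEs and infusion-related AESIs, events per infusion given, using the infusion counts already planned in SAP 10.
3. For PCS values, DILI criteria and C-SSRS, a split of the Extension into Weeks 25-48 and Weeks 49-72, divided at the start of the Visit 14 infusion. Each block has 24 weeks and 2 infusions (V8 and V11; V14 and V17), 2 scheduled laboratory, ECG and C-SSRS visits and 4 vital-sign slots, matching the Placebo-controlled Period. The same split can serve for adverse events as an alternative that avoids the constant-rate assumption.
4. A sentence in the addendum that the Extension population is selected for having tolerated earlier treatment, which neither the rates nor the blocks correct.

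The cost is SAP wording and more addendum output; all the data are already collected. The patient-year figures carry a constant-rate assumption, which suits infusion-timed events poorly; that is why those are given per infusion.
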